1.3 Design and methodology

1.3.1 Research design and General Methodological Approach

We propose a randomized controlled double-blinded trial comparing oral gabapentin 600 mg to placebo among patients undergoing outpatient same-day dilation and evacuation under moderate sedation. We propose to give the study drug (gabapentin or placebo) shortly after the initiation of same-day cervical preparation and a minimum of one hour prior to D&E. The primary study outcome is maximum pain during D&E as recorded by 100-mm VAS (Table 1). Secondary outcomes include total doses of IV sedation, pain at three time points during D&E, perioperative pain, anxiety, nausea, vomiting, patient satisfaction with pain management, oxygen saturation during moderate sedation, and administration of sedation reversal agents. We will also contact patients by phone on post-operative day 1 (POD1) to assess for prolonged or delayed side effects, adverse events and overall satisfaction with pain control.

Study medications will be administered by study staff, Planned Parenthood of Metropolitan Washington DC (PPMW) staff, or MedStar Washington Hospital Center (MWHC) staff after initiation of cervical preparation. The MedStar Health Research Institute (MHRI) pharmacy will prepare identical capsules containing gabapentin 600 mg or methylcellulose placebo. The pharmacy will package the capsules in sequentially numbered opaque sealed envelopes according to a computer-generated 1:1 randomization scheme prepared by MHRI. Study staff involved in administering medications and assessing outcomes, clinical staff (health care associates, nurses, physicians), and participants will be blinded to randomization assignment. Randomization assignment will only be revealed at the time of data analysis or in the case of a serious adverse event. As there is no standard or optimal dose of pre-operative gabapentin, we have chosen to use a dose of 600 mg with the aim of maximizing pain relief while minimizing the sedative effect. This is the same dose currently being investigated during first-trimester abortion at Emory University.

Administration of analgesics, anesthetics, and anti-emetics will be standardized. Patients will generally receive the following oral pre-procedure regimen: naproxen 500 mg, ~~tramadol 50 mg,~~

alprazolam 0.25 mg, promethazine 25 mg, and azithromycin 500 mg. Medications may be adjusted per provider judgement and patient characteristics, such as allergies. At the time of D&E, providers will administer a paracervical block using 20 mL of 1% lidocaine with 4 units vasopressin. Initial doses of moderate sedation at both sites will be 1 mg midazolam and 50 mcg fentanyl. Additional doses are sometimes required intraoperatively to achieve adequate pain relief and will be left to provider discretion. Total doses of moderate sedation will be capped at 5 mg midazolam and 200 mcg fentanyl. Total doses of midazolam and fentanyl will be documented.

Assessments and tools:

Pain will be assessed using 100-mm VAS. We will assess pre-operative pain using VAS while the patient awaits moderate sedation administration in the procedure room. We will assess intra-operative pain at the following time points: within one minute after speculum placement, within one minute after the initiation of uterine suction aspiration, and within one minute after speculum removal. An assessment of “maximum” intra-operative pain will be made 3- 5 minutes after speculum removal. VAS will be used to assess post-operative pain 30 minutes (range 20-40 minutes) after the procedure. Assessments of anxiety will be made using 20-items of state anxiety from the State Trait Anxiety Inventory (STAI), a validated tool for measurement of anxiety that is used frequently in abortion research [19], [20]. Anxiety will be assessed prior to administration of moderate sedation and 30 minutes post-procedure. Nausea, vomiting, and satisfaction with pain control will be assessed using 5-point Likert scale prior to the administration of moderate sedation and 30 minutes post-procedure. Lowest intra-operative oxygen saturation as measured via pulse oximeter and administration of reversal agents will be recorded. Adverse events will be monitored and include, but are not limited to, seizure-like activity, need for sedation reversal agent, respiratory depression (oxygen saturation <90%), use of uterotonics, aspiration of emesis, or transfer to hospital. Overall satisfaction with pain control will also be assessed on POD1 using a 5-point Likert scale. Participants will receive financial compensation in the form of a \$40 gift card on the day of the procedure for their time and participation. After completion of the phone assessment on POD1, participants will be mailed a \$10 gift card.

Table 1: Assessments

Time	VAS	STAI	Nausea, vomiting, and satisfaction 5-point Likert
Pre: Prior to moderate sedation	X	X	X

Intra-op: Within 1 minute after speculum insertion	X		
Intra-op: Within one minute after initiating uterine aspiration	X		
Intra-op: Within 1 minute after speculum removal	X		
Max pain experienced during abortion procedure, assessed 3-5 min after speculum removal (Primary outcome)	X		
Post: 30 min after D&E completion	X	X	X
POD1			X (satisfaction only)

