1.3.3 Subject recruitment and allocation

A total of 130 participants will be recruited from two sites at the time of abortion provision: MedStar Washington Hospital Center Family Planning and Preventative Care (MWHC) and Planned Parenthood of Metropolitan Washington DC (PPMW). PPMW has a diverse patient population, with a

majority of women being African American and age 20-29 years old. We will recruit from the PPMW clinic on the day they provide second trimester termination procedures. MWHC patients are generally referred from their general obstetrician’s office or self-referred for abortion and are seen in a private outpatient office. We will recruit eligible patients on days when we are not recruiting at PPMW. Baseline characteristics of the outpatient center at WHC and at PPMW in 2012 are shown below:

Table 2: Patient demographics

Age (years)	WHC	PPMW
<20	4%	12%
20-24	11%	38%
25-29	11%	25%
30-39	68%	21%
40 or more	6%	5%
Race		
Black, non-Hispanic	22%	65%
White, non-Hispanic	61%	16%
Hispanic	11%	8%
Multiracial	0%	8%
Other/unknown	6%	3%

In both recruitment settings, D&E is offered as a same-day procedure under moderate sedation with fentanyl and midazolam. Standard care at both sites includes cervical preparation with misoprostol and/or osmotic dilators, initiated at least two hours prior to D&E. Patients will be recruited after gestational age is confirmed to be 14 through 19 weeks, after eligibility for moderate sedation is confirmed, and after patients have provided informed consent for surgical abortion (Appendix A). This occurs after the patient has completed ultrasound, counseling, lab studies, and documentation of medical history. Patients will generally be recruited after initiation of cervical preparation, as this is a time when clinic flow will not be disrupted by study recruitment. Some participants may be recruited before cervical preparation initiation, as clinic flow permits, but no participant will receive study medications until after cervical preparation has begun.

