Patients will be approached by study staff in a private room where eligibility will be assessed and consent will be obtained. A detailed explanation of the study will be provided and written informed consent will be obtained (Appendix B). The patient will be given a copy of her signed informed consent. After the consent is signed, eligibility for the study will be confirmed. Enrollment will be limited to 4 participants per site per day to minimize the impact on clinic flow. Permission to conduct this study has been obtained from the medical directors at both sites and will be approved by Planned Parenthood Federation of America research committee as well as the MHRI IRB.

A MHRI statistician not involved in the conduct of the study will produce the allocation sequence using a computer generated random sequence. The MedStar Health Research Pharmacy will prepare sequentially numbered sealed opaque allocation packets containing the appropriate study medications within opaque capsules. The packets will not be assigned to a participant until eligibility is confirmed. Randomization assignment will only be revealed at the point of data analysis, serious adverse event, or if interim assessment is needed.

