1.3.5 Admission procedure

After eligibility has been confirmed and informed consent has been obtained, participants will complete a questionnaire assessing demographic information and medical history (Appendix C). Relevant baseline characteristics including age, gravidity, parity, race, ethnicity, and weeks of gestation will be collected. We will also document pre-existing psychiatric disorders such as depression, anxiety, bipolar disorder and chronic pain syndromes.

She will then be assigned to the next sequentially numbered randomization packet. After initiation of cervical preparation, the participant will consume the study drug from the packet with water or clear juice. Time of administration will be recorded on the patient's chart and will occur at least one hour before the planned procedure. All medications given throughout the clinic experience will be recorded. Method(s) of cervical preparation will be recorded. Antibiotic, anti-emetic, and analgesic administration will be standardized but medications may be adjusted to the need of each woman to accommodate patient characteristics such as allergies and without regard to her enrollment in this study.

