1.3.11 Number of subjects and statistical power

Based on the literature which showed a mean pain score of 3.6 with IV sedation [7], and considering that D&E is expected to be more painful than first-trimester uterine aspiration, we estimate a mean pain score of 45 and a SD of 25 using a 100-point scale for patients in the control group. 30% reduction in pain has been accepted as clinically significant [24]. With 80% power and alpha of 0.05, we will need to include 59 participants in each arm (118 total) to detect a decrease of 13 points on a 100-point scale, approximately 30% reduction in pain. As the primary outcome is assessed on the same day as enrollment, we do not expect significant loss to follow up. Accounting for the possibility of withdrawals or incomplete data, we plan to enroll 130 women. Enrollment of 3-5 patients per week will allow recruitment to be completed in approximately 26-43 weeks (6-10 months).

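### Two sites with different populations, but blocking, site stratification and packet series are not specified, and the primary t-test has no site term

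*Combined protocol and SAP*

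**What the plan says.** Three places in the combined protocol and SAP describe allocation.

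- Section 1.3.1: a "computer-generated 1:1 randomization scheme prepared by MHRI", packed by the pharmacy in numbered, sealed, opaque envelopes.
- Section 1.3.3: an independent statistician "will produce the allocation sequence using a computer generated random sequence".
- Section 1.3.5: after consent and the questionnaire, "She will then be assigned to the next sequentially numbered randomization packet".

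None mentions blocks, strata or a separate list per site. None says whether the clinics share one packet series.

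On sites, Section 1.3.3 states: "A total of 130 participants will be recruited from two sites at the time of abortion provision". It gives no target per site. Of the hospital clinic it says only: "We will recruit eligible patients on days when we are not recruiting at PPMW". Table 2 (2012 figures) gives age 30–39 as 68% at the hospital clinic and 21% at the Planned Parenthood clinic, Black non-Hispanic as 22% and 65%, and White non-Hispanic as 61% and 16%.

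Section 1.3.10 compares the primary outcome by t-test, or non-parametrically if appropriate. Baseline characteristics are to be examined for confounding and interaction. Site is not named there or among the baseline characteristics in Section 1.3.5, and the forms in Appendices C to G have no explicit site field.

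**The concern.** Site could plausibly relate to reported pain. Patients and referral routes differ. Cervical preparation may be misoprostol, dilators or both, and additional sedation is left to the provider. If site is related to pain and the arms differ by chance in site mix, part of the observed treatment difference is a site difference. Stratified allocation or a site term in the model would remove that component, and the plan specifies neither. A confounding check made after the data are in is weaker than a prespecified term, because the decision to adjust then depends on what is seen.

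**Working it through.** **Inputs.** From Sections 1.3.3 and 1.3.11: N = 130; target difference 13 mm; "we estimate a mean pain score of 45 and a SD of 25 using a 100-point scale"; 80% power; alpha 0.05; 59 per arm. Assumed, because the documents do not give them: simple randomisation, the site split, and a site difference in mean pain (D) of 5, 10 or 15 mm.

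**1. The plan's own figure.** n per arm = 2 × [25 × (1.960 + 0.842) / 13]² = 58.05, rounded up to 59. This reproduces the stated figure with a two-sided test. Noncentral-t power is 80.0% at 59/59 and 83.7% at 65/65.

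**2. Arm sizes.** With all 130 evaluable, power is 83.7% at 65/65, 83.3% at 72/58 and 82.6% at 76/54. A 72/58 split therefore costs 0.4 points. Averaged over simple randomisation, power is 83.4%.

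**3. Site mix.** Under simple randomisation the between-arm difference in site share has SD of about √[p(1−p) × 4/130]. For p = 0.5 this is √(0.25 × 4/130) = 0.088. Simulation gives:

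| Site split | SD (points) | P(≥10 points) | P(≥15 points) |
|---|---|---|---|
| 50/50 | 8.8 | 25% | 9.5% |
| 70/30 | 8.1 | 22% | 6.6% |
| 90/10 | 5.3 | 6% | 0.4% |

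**4. Effect on the estimate.** Shift = D × imbalance. At 50/50 the 97.5th percentile of imbalance is 17.1 points, so the shift is 0.9, 1.7 or 2.6 mm for D = 5, 10 or 15. The standard error at 65/65 is 25 × √(2/65) = 4.4 mm, so even this tail case is 0.2 to 0.6 of a standard error. It can go either way and averages zero.

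**5. Gain from a site term.** Take 25 as the total SD. At a 50/50 site split, between-site variance is D² × 0.25, and the within-site SD is √(625 − 0.25D²). With site balanced across arms at 65/65:

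| D (mm) | Share of variance | Within-site SD | Power |
|---|---|---|---|
| none adjusted | – | 25 | 83.7% |
| 5 | 6.25/625 = 1% | 24.87 | 84.1% |
| 10 | 25/625 = 4% | 24.49 | 85.1% |
| 15 | 56.25/625 = 9% | 23.85 | 87.0% |

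**6. If site is adjusted for but not stratified.** Residual imbalance inflates the adjusted variance by 1/(1 − r²). At 50/50 with equal arms, r equals the imbalance, so a typical r² is 0.0884² = 0.008. Dividing each within-site SD by √(1 − 0.008) = 0.996 gives power of 83.8%, 84.9% and 86.7% for D = 5, 10 and 15, and 83.4% if the sites do not differ at all.

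**The case against.** The documents are silent on blocking and stratification; they do not exclude them. A reader might infer that the sequence is plain, with no blocks or strata. The text does not support that: a statistician's 1:1 scheme could be blocked, and each site could have its own packets. Every imbalance probability above is therefore conditional. The silence is also judged on the text supplied, from which some pages are missing.

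A reader might also infer that an arm smaller than 59 leaves the trial short of power. It does not. The 59 belongs to two equal arms totalling 118, and the trial enrols 130. With all 130 evaluable, power falls below 80% only at 85/45 or worse, which has a probability of about 0.06% under simple randomisation. With only 118 evaluable, a 70/48 split gives 78.6% instead of 80.0%, which is still a small loss.

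A third tempting reading is that chance site imbalance biases the result. It does not: the unadjusted t-test remains valid, and if the SD of 25 is a total SD, its standard error already contains the between-site variance.

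Table 2 describes each centre's patients in 2012, not women eligible for this trial, and nothing in the documents links age or race to intraoperative pain. Starting sedation doses and dose caps are common to both sites. The confounding check in Section 1.3.10 could pick up site, although site is not named.

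All of this stands and limits the point to precision and specification. It does not explain why the sequence method and the role of site are left unstated.

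**Conclusion.** The point holds as a gap in specification with a modest, nearly free gain in precision. The plan recruits at two clearly different sites, does not state how the sequence is built or how packets are shared, and names no site term in the primary analysis. If randomisation is simple, a site-mix difference of 10 or more points has a 22–25% chance at site shares of 30–70% and about 6% at 90/10. The consequence is extra variance, not bias. Adjusting for site is worth 0.4 to 3.3 power points (83.7% to between 84.1% and 87.0%) if the sites differ by 5 to 15 mm and site is balanced across arms. Without stratification it is worth about 0.1 to 3.0 points. If the sites do not differ, an adjusted but unstratified analysis costs about 0.3 points. The site split and the site difference in pain are assumptions. The validity of the planned comparison is not in question.

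**What to change.** 1. Record site for every participant. Replace the unadjusted primary t-test in Section 1.3.10 with a linear model of maximum-pain VAS on treatment and site, fixed in writing before unblinding. This costs one degree of freedom and can still be done after enrolment has started. If the non-parametric alternative is kept, use a site-stratified rank test.
2. State in Section 1.3.3 how the sequence is generated and whether each site has its own packet series. If enrolment is under way, document the method actually used.
3. If enrolment has not begun, stratify allocation by site in randomly varying permuted blocks, with a separate packet series per site. Keep block sizes in a document that site staff do not see. The pharmacy already prepares numbered packets, so the extra work is a second series.

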12) Are you having an abortion because of a fetal diagnosis?

- NO
- YES. Please describe: _____

INTRODUCTION TO VISUAL ANALOG SCALE

For these questions, we are going to ask you to make an X on a line. For example, let's say you are asked how much you like Oreo cookies:

How much do you like Oreo cookies? (make an X on the line)

very little _____ very much

You answer the question by making an "X" on the line according to how much you like or dislike Oreo cookies.

If you liked Oreo cookies a lot, then you might make an "X" on the line like so:

very little _____ X _____ very much

If you liked Oreo cookies more than life itself(!), then you might make an "X" on the line like so:

very little _____ X _____ very much

If you hated Oreo cookies, then you might make an "X" like so:

very little X _____ very much

If you thought Oreo cookies were just "OK," then you might make an "X" like so:

very little _____ X _____ very much

The idea is that if you like Oreo cookies, you make an "X" on the line closer to the phrase "very much;" the closer you make the "X," the more you are saying you like Oreo cookies. If you don't like Oreo cookies, you make an "X" on the line closer to the phrase "very little;" the closer you make the "X," the more you are saying you don't like Oreo cookies.

13) How much do you like Oreo cookies? (make an X on the line)

very little _____ very much

14) How much pain do you experience with your menstrual periods? (make an X on the line)

very little _____ very much

15) How much pain do you anticipate having during your procedure? (make an X on the line)

very little _____ very much

16) How much pain you are experiencing at this time? (make an X on the line)

very little _____ very much

Medical Record Review

1) Date of birth (MM/DD/YYYY): ____ / ____ / ____

2) Gestational age: ____ weeks ____ days

3) Height: ____

4) Weight: ____ kg/lbs

5) Medications administered:

Type: (include antibiotics, misoprostol, uterotonics, pain and nausea medication)	Route -Oral -IV -Rectal -Vaginal -Paracervical	Dose	Timing - Pre-op - Intra-op - Post-op	Time	Notes
 Azithromycin	 Oral	 500 mg	 Pre		
 Alprazolam	 Oral	 0.25 mg	 Pre		

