Appendix D: Pre-Operative Assessments

Subject ID:	Date:	Time:	Interviewer:
-------------	-------	-------	--------------

- 1) How much pain you are experiencing at this time. (make an X on the line)

very little _____ very much

2) How satisfied are you with your pain relief at this time?	Very unsatisfied 1	Somewhat unsatisfied 2	Neutral 3	Somewhat satisfied 4	Very Satisfied 5
3) How much nausea are you experiencing at this time?	No nausea 1	Very little 2	Mild 3	Moderate 4	Severe nausea 5
4) How much vomiting are you experiencing at this time?	No vomiting 1	Very little 2	Mild 3	Moderate 4	Severe vomiting 5

- 5) Have you experienced any other symptoms, besides pain, since you were given the study medications?
- NO
 - YES. If yes, please describe: _____

State Trait Anxiety Inventory (STAI) – State Items

Read each statement and select the appropriate response to indicate how you feel right now, that is, at this very moment. There are no right or wrong answers. Do not spend too much time on any one statement but give the answer which seems to describe your present feelings best.

		Not at all	A little	Somewhat	Very much so
1	I feel calm	1	2	3	4
2	I feel secure	1	2	3	4
3	I feel tense	1	2	3	4
4	I feel strained	1	2	3	4
5	I feel at ease	1	2	3	4
6	I feel upset	1	2	3	4
7	I am presently worrying over possible misfortunes	1	2	3	4
8	I feel satisfied	1	2	3	4
9	I feel frightened	1	2	3	4
10	I feel uncomfortable	1	2	3	4
11	I feel self confident	1	2	3	4
12	I feel nervous	1	2	3	4
13	I feel jittery	1	2	3	4
14	I feel indecisive	1	2	3	4
15	I am relaxed	1	2	3	4
16	I feel content	1	2	3	4
17	I am worried	1	2	3	4
18	I feel confused	1	2	3	4
19	I feel steady	1	2	3	4
20	I feel pleasant	1	2	3	4

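### Anxiety, nausea and vomiting are first measured after the study drug, so these Objective 3 outcomes, unlike pain, have no pre-dose value to adjust for

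*Combined protocol and SAP*

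**What the plan says.** All references are to the combined protocol and SAP.

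- **Outcomes.** Objective 3 (section 1.1.2) expects gabapentin to lower pain, anxiety, nausea and vomiting both before and after the operation. The pre-operative scores are therefore outcomes in their own right.
- **Schedule.** Section 1.3.1 states: "Anxiety will be assessed prior to administration of moderate sedation and 30 minutes post-procedure". For the Likert items it states: "Nausea, vomiting, and satisfaction with pain control will be assessed using 5-point Likert scale prior to the administration of moderate sedation and 30 minutes post-procedure". The earliest row of Table 1 is "Pre: Prior to moderate sedation"; there is no row before the study drug.
- **Dosing.** The study drug is given "shortly after the initiation of same-day cervical preparation and a minimum of one hour prior to D&E". Section 1.3.5 places the Appendix C questionnaire first, then packet assignment, then dosing.
- **Pre-dose form.** Appendix C item 16 is a VAS headed "How much pain you are experiencing at this time". Appendix C also records anxiety diagnosis and treatment, benzodiazepine use and anticipated pain. It has no STAI, nausea or vomiting item.
- **First post-dose form.** Section 1.3.6 places Appendix D just before sedation starts. Its item 5 confirms that it follows dosing: "Have you experienced any other symptoms, besides pain, since you were given the study medications".
- **Analysis.** Section 1.3.10 compares secondary outcomes between arms by t-test or Chi-square. It also says that baseline characteristics will be examined for confounding and interaction, without listing them.

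**The concern.** Pain has a pre-dose score; three other outcomes in the same objective do not. Each of them has two scheduled ratings, and both come after treatment has begun.

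This has three consequences. First, variation in how anxious women are on arrival stays in the error term, apart from whatever the recorded history explains. Second, a chance difference between arms in state anxiety at entry cannot be seen or adjusted for. Third, no valid change from baseline can be computed for these outcomes.

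There is also a smaller trap. The Appendix D rating carries the label Pre, and the analysis section does not say which variables count as baseline. Section 1.2 cites a meta-analysis linking pre-operative gabapentin to less anxiety and nausea. On the plan's own reasoning, then, the Appendix D score may already contain drug effect.

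**Working it through.** **1. Order of the forms.** Sections 1.3.5 and 1.3.6 give this sequence: Appendix C, packet assignment, study drug, Appendix D, sedation and D&E, Appendix F. STAI, nausea and vomiting appear on D and F only. Current pain appears on C, D and F.

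**2. The plan's own figure.** Section 1.3.11 gives SD 25, difference 13, power 80% and alpha 0.05. With a two-sided test, n per arm = 2 × [(1.960 + 0.842) × 25 / 13]² = 58.05, rounded up to 59, or 118 in total. This matches the plan (a one-sided test would need 46). It concerns the primary pain outcome; the plan states no power for anxiety, nausea or vomiting.

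**3. Detectable STAI difference without a baseline.** In SD units it is (1.960 + 0.842) × √(2/n):
- 59 per arm: 2.802 × √(2/59) = 0.52 SD
- 65 per arm (130 enrolled): 2.802 × √(2/65) = 0.49 SD

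**4. Detectable difference with a pre-dose score in ANCOVA.** Residual variance is multiplied by 1 − r², so the detectable difference is multiplied by √(1 − r²). Here r is the within-arm correlation between the pre-dose and later score. The documents give no value; 0.4 to 0.7 is assumed.

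| r | 1 − r² | Variance cut | Equivalent n, 1/(1 − r²) | Detectable, 59 per arm | Detectable, 65 per arm |
|---|---|---|---|---|---|
| 0.4 | 0.84 | 16% | 1.19 | 0.47 SD | 0.45 SD |
| 0.5 | 0.75 | 25% | 1.33 | 0.45 SD | 0.43 SD |
| 0.6 | 0.64 | 36% | 1.56 | 0.41 SD | 0.39 SD |
| 0.7 | 0.51 | 49% | 1.96 | 0.37 SD | 0.35 SD |

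**5. Chance imbalance at entry.** The 95% limit for a chance difference in mean state anxiety is 1.96 × √(2/65) = 0.34 SD with 65 per arm, or 1.96 × √(2/59) = 0.36 SD with 59. The unadjusted test already allows for this in its standard error, but the difference could not be inspected or adjusted for.

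**6. If the Appendix D score were taken as a baseline.** Assume, for illustration only, a true drug effect of 0.5 SD at both Appendix D and Appendix F. A change score would estimate 0.5 − 0.5 = 0. ANCOVA would estimate 0.5 − r × 0.5, where r is now the correlation between the D and F scores: 0.30, 0.25 or 0.15 SD for r = 0.4, 0.5 or 0.7. The plan does not schedule either analysis; this shows only why a sentence ruling them out is useful.

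**The case against.** The strongest reply is that nothing planned is invalid. The trial is randomized 1:1 and double-blind. An unadjusted between-arm test is unbiased, and its type I error already covers chance imbalance. To test whether gabapentin lowers pre-operative anxiety, the score has to be taken after dosing. All of this stands.

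A reader might infer from the label Pre that the plan treats the Appendix D STAI as a baseline and so removes part of the drug effect. The documents do not support this. Section 1.1.2 names the pre-operative scores as outcomes, section 1.3.10 plans no change score, and the baseline characteristics listed in section 1.3.5 do not include STAI. The most that can be said is that the text does not expressly exclude such use.

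A reader might also infer that Appendix D always falls at least an hour after dosing. The documents do not guarantee that gap: the hour runs to D&E, or to the planned procedure in section 1.3.5, and Appendix D comes before both. It is post-dose in any case.

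The size of the gain is also open to challenge. The correlation is assumed, and alprazolam, the sedation and the procedure itself may lower it. Table 2 shows that the sites differ in age and race but says nothing about anxiety. Anxiety history, benzodiazepine use and anticipated pain are already recorded before dosing and may explain some of the variation. They remain proxies, not a pre-dose measure of the outcome.

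Finally, the added items must fit between consent and dosing. Because recruitment may come before or after the start of cervical preparation, the baseline would not be taken at one uniform point. It would still precede packet assignment, which is what a valid covariate needs.

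**Conclusion.** The point holds as a precision and clarity issue, not as a bias. STAI, nausea and vomiting have no pre-dose value, while pain does. For STAI, a pre-dose score would cut residual variance by 16% to 49% if the correlation lies between 0.4 and 0.7. At 0.5 with 59 per arm, the detectable difference improves from about 0.52 to 0.45 SD. That range rests wholly on the assumed correlation. For the 5-point nausea and vomiting items the gain is unquantified and probably smaller.

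The documents do not support concluding that the planned comparisons are invalid or that the plan subtracts a drug effect. The primary outcome is untouched. This is a cheap improvement of minor weight, confined to secondary outcomes.

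**What to change.** 1. Add the 20 STAI state items and the Appendix D nausea and vomiting items to Appendix C, next to the current-pain VAS, to be completed before the packet is assigned.
2. Add a row to Table 1, *Baseline: before study drug*, covering VAS, STAI, nausea and vomiting.
3. In section 1.3.10, specify that the Appendix D and Appendix F STAI scores are each compared between arms by ANCOVA adjusted for the pre-dose STAI score.
4. In the same section, state that Appendix D scores are post-dose outcomes and will not be used as baseline covariates or for change scores.

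The cost is a few more minutes per participant between consent and dosing, and one more repetition of the STAI. The items already exist in the protocol, and no extra staff or procedure is needed. If the added page is judged too much, item 4 can be adopted alone at no cost; it closes the ambiguity but recovers no precision.
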